3.2.1.3 Other efficacy analyses

Analysis of other efficacy endpoints will be performed on the ITT population.

3.2.1.3.1 Time to first bowel movement

The time to first bowel movement defined as the time between first intake of prescription and first bowel movement will be assessed and analysed using survival methods.

Table 9 specifies the event and censoring dates to be used in the analysis of time to first bowel movement.

Event	Time of event	Outcome
First bowel movement	Time of first bowel movement	Event
No bowel movement with colonoscopy	Time of colonoscope introduction	Censored
No bowel movement without colonoscopy	Time of first intake of prescription + 12 hours	Censored

 Table 9
 Time to First Bowel Movement (hours)

The distribution of time to first bowel movement will be estimated using the Kaplan-Meier (KM) product limit method. The results will be presented in a summary table and a KM plot will also be constructed.

The summary table will present by treatment group the numbers and percentages of subjects with occurrence of first bowel movement and the numbers and percentages of censored subjects. The summary will also include the median time to first bowel movement as well as the 25th and 75th percentiles with their two-sided 95 % CI, the percentage and 95 % CIs of subjects who had first bowel movement at 1, 1.5, 2, 2.5, 3, 3.5, 6, 9, 12, 15 and 18 hours from KM estimates.

Confidence intervals for median time to first bowel movement as well as the 25th and 75th percentile CIs will be calculated using the method of Brookmeyer and Crowley (1982) [5], which is the default method within SAS® version 9 and higher.

Kaplan-Meier curves will be constructed by treatment group and will display the number of subjects at risk at 1, 1.5, 2, 2.5, 3, 3.5, 6, 9, 12, 15 and 18 hours.

In addition, The treatment difference will be tested using a Cox proportional hazards model adjusted on country and the association with treatment will be further explored by presenting separate KM plots for each country.

The SAS Phreg procedure will be used as follows:

Proc Phreg Data=ADTTE(where=(PARAMCD='Time to first bowel movement' and ITTFL='Y'));

Class TRTP(ref='KLEAN-PREP') COUNTRYC(ref='Largest country'); Model AVAL*CNSR(1) = TRTP COUNTRYC / Ties = EXACT;

Run;

3.2.1.3.2 Wake-up during the night to have a bowel movement

The proportion of patients who wake-up during the night to have a bowel movement will also be tabulated by treatment group using frequency count with two-sided 95 % CI and analysed using Cochran-Mantel-Hænszel (CMH) chi-square for the proportions adjusting for country effect. The general association statistic will be used to assess the test significance.

The SAS Freq procedure will be used as follows:

proc freq data=ADCE(where=(CETERM='NIGHTLY BOWEL MOVEMENT' and ITTFL='Y'));

```
table COUNTRYC*TRTP*CEOCCUR / CMH;
```

run;

The difference of proportions with the 95 % CI and p-value will be summarised.

3.2.1.3.3 Satisfaction

The satisfaction will be also assessed through the question "If it was necessary, would you agree to undergo preparation with this product again?". It will also be tabulated by treatment group using frequency count with two-sided 95 % CI and analysed using Cochran-Mantel-Hænszel (CMH) chi-square for the proportions adjusting for country effect. The general association statistic will be used to assess the test significance.

The SAS Freq procedure will be used as follows:

```
proc freq data=ADQS(where=(QSTEST='AGREE TO TAKE PRODUCT AGAIN' and ITTFL='Y'));
```

table COUNTRYC*TRTP*QSORRES / CMH;

run;

The difference of proportions with the 95 % CI and p-value will be summarised.

3.2.1.3.4 Time between the last intake of fluids and the start of colonoscopy procedure

The time between the last intake of fluids and the start of colonoscopy procedure will be presented by treatment group using descriptive summary statistics (mean, SD, median, quartiles and ranges) and using a two-way analysis of variance (ANOVA) including treatment and country as well as the interaction between treatment and country, if it is significant (i.e. p < 0.10), as covariates using the following SAS code:

proc mixed data=ADEX(where=(PARAM='Time between the last intake of fluids and the start of colonoscopy procedure' and ITTFL='Y'));

class TRTP COUNTRYC;

38/62

model AVAL = TRTP COUNTRYC TRTP*COUNTRYC;
lsmeans TRTP / diff cl;

run;

The adjusted mean times, the adjusted treatment difference with their 95 % CI and the p-value of difference will be summarised.

In addition, this analysis will also be produced per country so that mean scores and the estimated treatment differences will also be provided per country using the following SAS code.

proc mixed data=ADEX(where=(PARAM='Time between the last intake of fluids and the start of colonoscopy procedure' and ITTFL='Y'));

```
class TRTP COUNTRYC;
model AVAL = TRTP COUNTRYC TRTP*COUNTRYC;
lsmeans TRTP*COUNTRYC / diff cl;
```

run;

3.2.2 Safety

The analyses of safety data will be performed based on the safety population.

3.2.2.1 Adverse events

All AEs will be coded according to MedDRA (last version used for coding during the study course) and will be classified by MedDRA preferred term (PT) and system organ class (SOC). AE listings will be presented by subject, SOC and PT for all AEs, serious AEs (SAEs) and AEs leading to withdrawal on the safety population.

A TEAE is defined as any AE that occurs during the active phase of the study if:

it was not present prior to receiving the first dose of IMP

or

• it was present prior to receiving the first dose of IMP but the intensity increased during the active phase of the study.

All TEAEs will be flagged in the AEs listings.

An overall summary table of all AEs will be presented with the number of AEs and the numbers and percentage of subjects with exact 95 % CI for each of the following categories:

- Any AEs,
- Any SAEs,
- Causality of SAEs,
- Any TEAEs,
- Intensity of TEAEs,
- Causality of TEAEs,
- Causality and intensity of TEAEs,
- Any TEAEs leading to death,
- Any TEAEs leading to withdrawal.

In the event of multiple AEs being reported by the same subject, each subject is counted for each intensity level, each causality level or each intensity and causality combined level. That means that the total number of subjects for all levels of intensity/causality might be higher

than the overall number of subjects with at least one AE. Related adverse events are those events with causality missing or related.

Incidence by SOC/PT of all reported TEAEs, related TEAEs, SAEs and TEAEs leading to withdrawal of study medication will be tabulated by treatment group and overall. In addition, summary tables by SOC/PT will present TEAEs by maximum intensity and drug relationship and will present TEAEs with incidence ≥ 2 %. And a summary table will present TEAEs by decreasing frequency of PT.

In the event of multiple occurrence of the same AE (same PT) being reported by the same subject, the maximum intensity (severe > missing > moderate > mild) and the most serious causality (related > not related) for each concerned PT will be chosen.

Moreover, the summary table will be duplicated by sex, age class and weight class, as well as the summary table of the incidence of TEAEs by SOC and PT.

Additionally, lesions suspected to be caused by colonic lavage (identified during the potential histological examinations of taken colonic biopsy specimens) will be recorded as AEs with the mention "suspected to be caused by colonic lavage" in the verbatim term by the investigator. The occurrence (Yes/No) of such AEs will be summarised for the treated subjects for whom the colonoscopy was done by treatment group and overall as well as the incidence by SOC/PT. The result of the biopsy will be listed.

3.2.2.2 Laboratory data

Laboratory data (haematology, biochemistry, and urinalysis) will be collected locally, while urine and blood sulfates will be assessed centrally. They will be listed in SI units and abnormal values will be derived using original normal ranges when available rather than using the investigator assessment and flagged (High [H], Low [L], clinically significant [C]), where applicable.

For eGFR, a threshold will be used and values $\geq 75 \text{ mL/min}/1.73 \text{ m}^2$ will be considered as normal, while the other ones will be considered as low.

Any unscheduled laboratory assessments will be flagged [U] in the listings.

A listing will present all values for a subject with at least one clinically significant abnormal laboratory value for biochemistry and urinalysis.

The baseline will be defined as the last measurement collected prior to the first dose of study drug.

As more than one laboratory will be involved in the study for the measurement of laboratory values, a standardisation method will be required in order to take into account the multiple reference ranges [6] for haematology, biochemistry, and urinalysis parameters with normal ranges. The site which has analysed the largest number of blood samples will be used as the reference site. The following formula will be used:

Standardised value =
$$L_R + (x - L_X) \frac{U_R - L_R}{U_X - L_X}$$

With L_R the reference site lower limit, U_R the reference site upper limit, L_X the local site lower limit, U_X the local site upper limit and x the non standardised value assessed in the local laboratory.

If a standardised value is negative it will be replaced by 0.

For pH and specific gravity no normal range is available, so no standardisation will be applied and no shift table will be provided.

For continuous urinalysis data and biochemistry, summary statistics will be presented by treatment group at each scheduled assessment for actual values and changes from baseline. Shift tables (based on local assessment) from baseline to each post baseline visit will be presented of the number and percentage of subjects with [low, normal or high values] at each visit.

For categorical urinalysis data (absent/trace/positive and normal/abnormal) frequency tables, by treatment group, will be presented at each scheduled assessment. Shift tables from baseline to each post baseline visit will be presented for the number and percentage of subjects with [normal, abnormal].

For blood and urine sulfates, summary statistics (mean, median, SD, minimum and maximum) will be presented by treatment group at each scheduled assessment for actual values and changes from baseline. In addition, mean plots by visit and treatment group will also be provided. Finally, sulfates are supposed to be collected fasted, and since some assessments have been performed non-fasted, a sensitivity analysis will be made to describe actual values and changes from baseline by treatment group and fasting status at each scheduled assessment.

3.2.2.3 Vital signs

Vital signs (including body weight and temperature, systolic and diastolic BP and HR) will be listed at each assessment by treatment group and subject. Any unscheduled vital signs will be flagged [U] in the listing.

Baseline values will be defined as the last vital signs measurement collected prior to the first dose of study drug.

Summary statistics for weight, temperature, BP and HR will be presented at each scheduled assessment for actual values and changes from baseline by treatment group.

Additionally, a frequency table describing the variations at post-baseline visits will be provided with the following categories:

• Weight: < -2 kg, [-2; -1 kg[, [-1; 1 kg[, [1; 2 kg] > 2 kg]

• BP and HR: < -20 unit, [-20; -10 unit[, [-10; 10 unit[, [10-20 unit] and > 20 unit.

3.2.2.4 Tolerability

Tolerability will be collected using a Symptom Scale after each dose of treatment for stomach cramping, stomach bloating and nausea on a paediatric 5-point scale (with 1=no symptom, 2=mild, 3=bothersome, 4=distressing and 5=severely distressing symptoms).

Each symptom after each dose will be described by treatment group using a frequency table. Additionally, each symptom after each dose will be summarised by treatment group as well as the total score (sum of the three symptoms).

Finally, each symptom after each dose will be summarised by treatment group and use of nasogastric tube (Yes/No), as well as sex, age class and weight class.

3.2.2.5 *Physical examination*

A listing with the date of examination and the status of the examination (performed/not performed) will be provided by treatment group, subject and examination date.

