# 2.2.2 Secondary Objectives

The secondary objectives of the study are as follows:

- To compare efficacy of Eziclen®/Izinova® versus Klean-Prep® on overall and segmental cleansing and colonoscopy quality indicators
- To assess compliance with preparation administration in both study arms
- To compare safety, acceptability and tolerability of Eziclen®/Izinova® versus Klean-Prep®

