**PAGE 59/103** 

All AEs will be coded according to the MedDRA and will be classified by MedDRA preferred term and system organ class. AE listings will be presented by subject, system organ class and preferred term.

Incidence of all reported TEAE and SAEs will be tabulated by treatment group and overall. In addition, summary tables will be presented by maximum intensity, drug relationship and AEs/TEAEs associated with premature withdrawal of study medication.

A TEAE is defined as any AE that occurs during the active phase of the study if:

- It was not present prior to receiving the first dose of IMP, or
- It was present prior to receiving the first dose of IMP but the intensity increased during the active phase of the study.

All TEAEs will be flagged in the AEs listings.

Concomitant medication will be coded by using World Health Organisation (WHO) Drug Dictionary and will be summarised by treatment group and overall with the number and percentage of subjects receiving concomitant medication by drug class and preferred drug name.

Summary statistics (mean, median, SD and range as appropriate) by treatment group and overall will be presented for vital signs, BP, HR, clinical laboratory tests (blood and urine sample), physical examination, etc. at each assessment with change from Baseline. For laboratory data, abnormal values will be flagged in the data listings and a list of clinically significant abnormal values will be presented. Shift tables will be presented of the number and percentage of subjects with low, normal or high values and normal or abnormal exams.

Frequency count with two-sided 95%CI when appropriate by treatment group and by overall will be presented for symptom questionnaire data (stomach cramping, stomach bloating and nausea) on a 5-point scale (see Table 11).

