1.2.2 Secondary objectives

The secondary study objectives are:

- To compare efficacy of Eziclen®/Izinova® versus Klean-Prep® on overall and segmental cleansing and colonoscopy quality indicators,
- To assess compliance with preparation administration in both study arms,
- To compare safety, acceptability and tolerability of Eziclen®/Izinova® versus Klean-Prep®.

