3.2 Analysis methods

Descriptive statistics will be presented as follows:

- Continuous variables: number of observations, number of missing data, mean, standard deviation (SD), median, quartiles, minimum and maximum;
- Dichotomous or categorical variables: frequency and percentage of each of the categories and number of missing data.

All study data will be at least presented in listings.

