3.2.1.2.9 Treatment acceptability

The treatment acceptability at the time of intake after dose 1 and after dose 2 will be assessed by a Treatment Acceptability Questionnaire completed by the caregiver or the subject using a

5-point scale questionnaire (see Table 4). It will be tabulated for each dose and overall (by taking the average of the 2 doses then considered as a score as follows: 1= Very badly accepted/unacceptable, 2= Badly but accepted, 3= Neither good nor bad, 4= Well accepted and 5= Very well accepted) by treatment group.

The acceptability for each dose will be assessed using frequency count with two-sided 95 % CI and analysed using Cochran-Mantel-Hænszel (CMH) chi-square for the proportions adjusting for country effect. The row mean scores differ statistic will be used to assess the test significance.

The SAS Freq procedure will be used as follows:

```
proc freq data=ADQS(where=(QSCAT='TREATMENT ACCEPTABILITY
QUESTIONNAIRE' and PARAMCD in ('TRTA011','TRTA012') and ITTFL='Y'));
table COUNTRYC*TRTP*QSORRES / CMH;
by QSGRPID;
```

run;

The p-value of difference will be summarised.

The overall acceptability will be presented by treatment group using descriptive summary statistics (mean, SD, median, quartiles and ranges) and using a two-way ANOVA including treatment and country as well as the interaction between treatment and country, if it is significant (i.e. p < 0.10), as covariates using the following SAS code:

```
proc mixed data=ADQS(where=(QSCAT='TREATMENT ACCEPTABILITY QUESTIONNAIRE' and PARAMCD='TRTA01' and ITTFL='Y'));
```

```
class TRTP COUNTRYC;
model COMPLIPCT = TRTP COUNTRYC TRTP*COUNTRYC;
by ASPID;
```

lsmeans TRTP / diff cl;

run;

The adjusted mean score, the adjusted treatment difference with their 95 % CI and the p-value of difference will be summarised.

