5 CHANGES FROM PROTOCOL

It was planned in the protocol to tabulate the efficacy and safety (laboratory, vital signs and tolerability) results by treatment group and overall, but this is not relevant to pool them so only description by treatment group will be provided.

48/62

It was planned in the protocol to include the interaction treatment*country in the ANOVAs of the applicable secondary endpoints, but as for the primary analysis the interaction will rather be investigated and kept only if it is significant.

It was not planned in the protocol to perform secondary analyses on mITT and PP, but it was decided to take into account the significant difference in terms of number of patients between ITT and the mITT and PP populations in order to assess the robustness of the results.

It was not planned in the protocol to present the primary endpoint according to subgroups (age class, weight class and sex), but descriptive statics have been added to explore the primary results.

It was not planned in the protocol to describe the time between the last intake of fluids and the start of colonoscopy procedure, but as this factor has been shown to be a major contributor to quality in adult patients it has been decided to add this description (Hassan et al.).

It was planned in the protocol to exclude from the PP population all subjects with major deviations, but some major deviations do not have an impact on the analyses, so they have been identified in the Protocol Deviation Document and the definition of the PP population has been updated to only consider the deviations having an impact on the analyses.

6 **REFERENCES**

- 1 Schwartz GJ and Work DF. Measurement and Estimation of GFR in Children and Adolescents. Clin J Am Soc Nephrol. 2009; 4: 1832–1843
- 3 International Conference on Harmonisation (ICH) E9 and Federal register Vol. 63, No. 179 (September 1998).
- 4 SAS, Version 9.3. SAS Institute Inc., Cary, NC, USA, 2012.
- 5 Brookmeyer, R. and Crowley, J. (1982), "A Confidence Interval for the Median Survival Time" Biometrics, 38, 29–41.
- 6 Karvanen J. The statistical basis of laboratory data normalization. Drug Information Journal. 2003;37(1):101-107.

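### SAP 3.2.2.4 describes symptom scores by arm only, so the tolerability part of a comparative secondary objective has no specified between-arm difference or confidence interval

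*SAP*

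**What the plan says.** Protocol 2.2.2 lists as a secondary objective "To compare safety, acceptability and tolerability of Eziclen®/Izinova® versus Klean-Prep", and SAP 1.2.2 repeats it.

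The tolerability measure is the Symptom Scale in protocol 8.6: stomach cramping, bloating and nausea, each scored from 1 (none) to 5 (severely distressing), collected after each of the two doses. Both documents class it as a safety and tolerability variable (protocol 3.2.2.2, SAP 3.1.3).

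For its analysis, protocol 10.4.7 states: "Frequency count with two-sided 95%CI when appropriate by treatment group and by overall will be presented for symptom questionnaire data".

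SAP 3.2.2.4 states: "Each symptom after each dose will be described by treatment group using a frequency table". It adds summaries by arm of each symptom and of a total over the three symptoms, and breakdowns by nasogastric tube use, sex, age class and weight class. The general rule in SAP 3.2 for such data is "Dichotomous or categorical variables: frequency and percentage of each of the categories and number of missing data", with no interval.

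SAP section 5 names tolerability among the results that lose their pooled column: "this is not relevant to pool them so only description by treatment group will be provided". It does not mention confidence intervals.

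Acceptability, another 5-point leaflet scale under the same objective, is compared between arms in SAP 3.2.1.2.9. Each dose gets a country-adjusted Cochran-Mantel-Haenszel analysis ("The row mean scores differ statistic will be used to assess the test significance"). The average over doses gets a two-way ANOVA giving an adjusted treatment difference with a 95% interval.

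**The concern.** An objective worded as a comparison needs an estimate of the contrast and of its uncertainty. As SAP 3.2.2.4 is written, the reader gets two columns for each of six symptom-by-dose items (three symptoms, two doses) and for the total score, then the same again within subgroups, and has to judge the differences unaided.

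The question matters to this trial. Protocol 1.1 says that large-volume polyethylene glycol preparations are often poorly tolerated because of taste and volume, and the test regimen is the lower-volume one. Two items that SAP 3.2.1.3 classes only as other efficacy analyses, waking at night for a bowel movement and willingness to take the product again, each get a difference in proportions with a 95% interval and a p-value. A measure named in an objective gets less.

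The second issue is one of record. The protocol's qualified plan for intervals is not carried into the SAP text, and the section that exists to list departures does not list this one.

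**Working it through.** **1. The provisions side by side.**

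| Item | Within-arm 95% CI | Between-arm difference with CI |
|---|---|---|
| Symptom scale, protocol 10.4.7 | Yes, where appropriate | None |
| Symptom scale, SAP 3.2.2.4 | None stated | None |
| Acceptability per dose, SAP 3.2.1.2.9 | Yes | Test only |
| Acceptability overall, SAP 3.2.1.2.9 | Yes, adjusted means | Yes, country-adjusted |
| Adverse events, SAP 3.2.2.1 | Exact CI, overall summary only | None |

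The last row matters because protocol 8.6 requires any symptom scored 2 to 5 to be reported as an adverse event. That route gives incidence by arm and preferred term. Its intervals are attached to the overall summary categories, not to the three symptoms, and it contains no difference between arms.

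**2. The plan's own sample size.** The documents give no precision for tolerability, so the check starts from the stated size. Inputs (SAP 1.4.4): 85% success in both arms, margin 15 points, one-sided alpha 0.025, power 90%, dropout 4%.

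- n = (1.960 + 1.282)² × 2 × 0.85 × 0.15 / 0.15² = 119.1, rounded up to 120 per arm
- 120 / 0.96 = 125 per arm

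Both stated figures reproduce.

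**3. Precision of a symptom risk difference.** Half-width = 1.96 × √(2p(1−p)/n), with the same rate p assumed in both arms.

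| Assumed rate p | n = 125 | n = 120 |
|---|---|---|
| 20% | 1.96 × √(0.32/125) = 9.9 points | 10.1 points |
| 30% | 1.96 × √(0.42/125) = 11.4 points | 11.6 points |
| 50% | 1.96 × √(0.50/125) = 12.4 points | 12.7 points |

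**4. Precision of a difference in mean score.** Half-width = 1.96 × SD × √(2/n). At n = 125, assumed SDs of 0.8, 1.0 and 1.2 give 0.20, 0.25 and 0.30 points on the 1-to-5 scale.

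**5. Whether within-arm intervals would be enough.** Suppose, for illustration, symptom rates of 30% and 42% with 125 per arm.

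- Within-arm intervals: 22.0% to 38.0%, and 33.3% to 50.7%. They overlap.
- Difference: 12 points, with half-width 1.96 × √(0.30×0.70/125 + 0.42×0.58/125) = 11.8 points, so 0.2 to 23.8. This excludes zero.

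Restoring the protocol's intervals would therefore not do the work of an interval for the difference.

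**The case against.** The SAP is consistent within its own classes. Acceptability is a secondary efficacy endpoint, whereas the symptom scale is a safety endpoint, and adverse events, laboratory data and vital signs are likewise described by arm without formal contrasts. Section 5 says openly that tolerability will be described by treatment group. Measures close to the lower-volume rationale (acceptability, compliance, nasogastric tube need, willingness to repeat) already have between-arm analyses. SAP 3.2 provides n, mean and SD, so an unadjusted difference and interval can be computed from the tables.

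Much of that stands, and it limits the weight of the point. It does not remove the mismatch with an objective worded as a comparison. A hand-computed difference would also lack the country adjustment used elsewhere in the plan.

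Four stronger readings are tempting, and the documents do not support them:

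- A reader might infer that the SAP removed a planned between-arm estimate. It did not. The protocol's intervals were for counts within each arm and overall, and only where appropriate. The missing contrast is already missing in protocol 10.4.7.
- A reader might infer that the whole secondary objective goes unanswered. Acceptability, in the same objective, is compared. Only the tolerability component lacks a specified contrast.
- A reader might infer that these symptoms are analysed nowhere else. Scores of 2 or more also enter the adverse event tables.
- A reader might infer that the final tables will carry no intervals. The table templates are a separate document and the table list is redacted, so this cannot be determined. What can be said is that the SAP text specifies none.

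**Conclusion.** The point holds in a limited form. Neither the protocol nor the SAP text specifies a between-arm difference in symptom scores, although comparing tolerability is a stated aim. The absence from the SAP of the protocol's qualified within-arm intervals is a separate, undeclared departure and does not cause the missing contrast.

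The trial is large enough for the estimate to be informative: about ±10 to ±12 percentage points for a risk difference at 125 per arm. That rests on assumed common symptom rates of 20% to 50%, complete leaflets and an unadjusted Wald interval. The mean-score figures rest on assumed SDs. Incomplete leaflets would widen all of them.

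This is an inexpensive improvement to a descriptive secondary analysis. It has no bearing on the non-inferiority conclusion.

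**What to change.** In SAP 3.2.2.4:

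- For each symptom after each dose, and for the total score, add the between-arm difference in mean score with a two-sided 95% interval, adjusted for country. Use the two-way ANOVA already described for overall acceptability in SAP 3.2.1.2.9, including its rule for the treatment-by-country interaction. State whether the total is formed per dose.
- Run it on the safety population, as SAP 3.2.2 requires, and on the symptom score. The acceptability code selects the ITT population and names the compliance percentage as its response, so it should not be copied unchanged.
- If a proportion is also shown, use a score of 2 or more. Protocol 8.6 already uses this threshold for adverse event reporting.
- Label all of these as descriptive.

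For the within-arm 95% intervals of protocol 10.4.7, either restore them in SAP 3.2.2.4 or record their removal in SAP section 5.

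The cost is a few extra table columns and some programming, from data already collected. The drawback is a small number of additional descriptive comparisons (six symptom-by-dose items plus the total score) without multiplicity adjustment, which the label should make clear.
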